1. PURPOSE OF THE STUDY

a. Brief Summary

Continuous deep brain stimulation (cDBS) is an established therapy for the major motor signs in Parkinson's disease. Currently, cDBS is limited to "open-loop" stimulation, without real-time adjustment to the patient's state of activity, fluctuations and types of motor symptoms, medication dosages, or neural markers of the disease. The purpose of this study is to determine if an adaptive DBS system, responding to patient specific, clinically relevant neural or kinematic feedback, is more effective than continuous DBS on the motor Unified Parkinson's Disease Rating Scale (UPDRS III) and specific phenotypic measures in Parkinson's Disease.

b. Objectives

- 1). Determine the efficiency and effectiveness on PD signs of adaptive DBS (aDBS), triggered by patient-specific resting state neural activity, compared to continuous DBS (cDBS) using the UPDRS III and validated, high-resolution kinematic metrics of tremor, bradykinesia and freezing of gait (FOG).
- 2). Determine whether aDBS using a kinematic classifier pertinent to the patient specific phenotype is more efficient and/or effective on PD symptoms than aDBS using the using the patient's specific resting state neural classifier and/or cDBS.
- 3). Determine whether aDBS is more efficient and effective than cDBS in the optimized on medication state after six months of cDBS. We believe that the results of these experiments will make it possible for DBS to realize its full potential: a new generation of context-dependent, continuously adaptive DBS devices will have the ability to sense and modulate brain signals that are correlated to abnormal movement and will provide DBS therapy in different locations based on motor phenotype and state of activity.

c. Rationale for Research in Humans

The Nexus D and Nexus E systems are a newly developed technology allowing for bi-directional communication of information between the Activa® PC+S and a portable computer (PC). The PC will use real time neural and kinematic data to develop classifiers of the behavioral states of rest, tremor, and bradykinesia in PD. The investigator team will develop a series of algorithms (control policies) on the PC, which will inform the Activa® PC+S to turn ON or OFF (at a preset, safe and therapeutic setting) based on the kinematic or neural classifiers of PD. Using this established neural interface for the first time in human PD subjects, we will develop optimal patient-specific customized classifier and control policy algorithms. This will drive the future creation of closed-loop neuromodulation devices, embedding and automating sensing and stimulating platforms.

2. STUDY PROCEDURES

a. Procedures

For subjects not already enrolled in eprotocol 25916:

The patient will have a full physical and neurological examination to determine if it is appropriate for them to participate in this study. The clinical examination will include all the assessments used to evaluate if a patient with Parkinson's Disease is a good candidate for Deep Brain Stimulation surgery such as the Unified Parkinson's Disease Rating Scale. Additionally the patient will complete a Colombia Suicide Severity Scale Assessment at all study appointments to monitor for emergence of suicidal ideation or intent. After surgery, at the time of initial programming of the implanted neurostimulator. Patients will arrive in the off medication, OFF DBS state. Medication will be stopped 72 hours (extended release forms of dopamine agonists), 24 hours (regular form of dopamine agonists, controlled release forms of carbidopa/levodopa (CD/LD))and /or 12 hours (regular CD/LD, entacapone, rasagiline, selegiline, amantadine) before testing. The DBS system will not have been activated after the implantation.

The patient will undergo quantitative assessment of motor function in the Stanford Human Motor Control and Balance Laboratory. This will include quantitative digitography (QDG), quantitative range of motion analysis (Motus, LG G Watch, APDM System), tremorography, surface electromyography (EMG), and computerized dynamic posturography. Note: the subjects will be given practice trials in all of the quantitative tasks listed below, to ensure that the goal and the instructions of the task are understood before each assessment is performed.

1) repetitive wrist flexion-extension movement – rwFE; Using solid-state gyroscopes sensors (Motus Motion analysis system, LG Gwatch), that fit like a glove on the patient's hands and surface EMG sensors (Delsys Bagnoli 2 EMG System) placed on the skin above the wrist flexor and extensor muscles, the wrist movement and the muscle activation patterns will be quantified. Specifically, we will directly measure angular velocity and muscle activations. The patient's arm will be kept in a 90 degrees elbow flexion with forearm in a neutral position. The patient will perform a wrist flexion extension movement continuously from the "go" to the "stop" command. This test will assess the subject's bradykinesia state.

2) Tremorography; If the subject shows visible tremor of the hands, using the above mentioned angular velocity sensors, his/her resting or postural tremor behavior will be measured. Surface EMG sensors will be placed on the skin above the forearm muscles to capture the muscles activation pattern.

3) Repetitive alternating finger tapping (RAFT) keyboard task; RAFT is a computerized objective measure of movement velocity, speed of movement, and timing using an engineered keyboard (Quantitative Digitography) with two adjacent keys. The subject will alternatively finger tap (trill) on the keyboard. The test will be performed twice for each hand. The patient will be seated at a table on which the keyboard is placed with the hand that does not perform the task placed in his/her lap. The subject will be instructed to tap as fast as he/she can while maintaining the alternating movement. This test will quantify a set of movement abnormalities seen in Parkinson's Disease patients such as bradykinesia, freezing of movement, tremor or fatigue.

4) Stepping in place (SIP) task: the subject will be asked to step in place repetitively on two adjacent force plates (Smart EquiTest, Neurocom Inc) with each foot on each force plate. The subject will step at a speed similar with his/her normal walking. A baseline quiet stance will be acquired at the beginning and the end of the test. The subject will wear a harness to protect him/her from falling. The subject will wear sensors on their hands, arms, chest, trunk, feet and legs(APDM System). This test will quantify measures such as gait asymmetry, gait rhythmicity and left-right step coordination. These metrics may provide clues to underlying mechanisms involved in freezing of movement in PD. Our lab showed that the SIP metric has a high sensitivity (93%) and specificity (87%) for identifying freezers from non-freezers.

5) Unified Parkinson's Disease Rating Scale part III – Motor Examination (UPDRS III); The clinical motor assessment of the subject will be performed using the UPDRS III scale.

6) Gait Analysis: Subjects will wear sensors on their hands, arms, chest, trunk, feet and legs(APDM System). These tasks will quantify measures such as gait asymmetry, gait rhythmicity and left-right step coordination during subjects normal walking. Subjects may be asked to do regular forward walking as well as walking around obstacles (such as chairs, or small room dividers). These obstacles will be used in order to elicit freezing, which often occurs in constrained spaces. This type of freezing is frequently encountered in subjects' daily lives. Subjects will be monitored carefully by research team in order to ensure their safety and comfort.

7) Vibrotactile Stimulation: Patients will wear the gloves at rest or during kinematic movement analysis described above. If patients report pain or discomfort associated with the gloves, they will be taken off immediately. We do not anticipate this to occur.

The Local Field Potentials (LFP) from the DBS leads (electrodes) will be recorded during each kinematic test using the new sensing capabilities of the implanted neurostimulator (Activa PC+S). The LFP data will be retrieved from the neurostimulator during each kinematic test. The Nexus-D and Nexus E Systems will be used. Nexus-D and Nexus-E establishes a connection between the implanted neural electrodes and an external computer or their

implanted INS (the device in the patient's chest). This will allow for recording of neural activity in real time and adjustment of stimulation within clinically safe limits using prewritten algorithms that respond to real time neural and kinematic recordings. Real time STN LFP beta band power will be calculated both OFF DBS, and during "therapeutic" DBS. DBS will be applied through the electrode (1 or 2) that lies in between the electrode pair (0-2 or 1-3) with the greatest beta power. Therapeutic DBS: 100-190 Hz, 60 microsec at 3 volts OR the highest voltage <3V, that does not cause adverse effects. We will confirm that the therapeutic DBS will attenuate rest beta power by $\geq 50\%$. Patients will be seated at rest, or while performing self-paced repetitive wrist flexion-extension (WFE) for periods of 10 seconds, after a "Go" signal with angular velocity sensors attached to the hand. They may also do other tasks outlined above during closed loop stimulation.

Specific Aim 1a and 2a (SA1a, SA2a): Determination of classifier thresholds:

SA1. Resting state neural: ON and OFF triggers when the beta band power $> 50\%$ and $< 25\%$ respectively of the resting state beta power differential (beta power OFF – ON therapeutic DBS). SA2. Kinematic, tremor/bradykinesia: ON and OFF triggers when rectified tremor amplitude/root mean square angular velocity (Vrms) of WFE $> 50\%$ or $< 25\%$ of tremor/Vrms differential (OFF – ON therapeutic DBS) respectively.

Specific Aim 1b and 2b (SA1b, SA2b): Outcomes will be measured after 30 minutes of aDBS or cDBS. For neural and tremor aDBS, the Activa® PC+S will be updated in real time. For bradykinesia aDBS, the Activa® PC+S will be updated with the Vrms from 10 second epochs of WFE that the PD subject will perform every 2 minutes during the 30 minute trial. At the six month visit the subject will come in on medication on stimulation and SA1 and SA2 will be repeated in the then optimized on medication state. The control policy algorithms will be adjusted as necessary to adapt to this state (Specific aim 3, SA3) At the 1, 3, 6, 9 and 12 month visits subjects will come in off medication and on stimulation and will repeat quantitative assessment of motor function. This may include quantitative digitography (QDG), quantitative range of motion analysis (Motus, LG G Watch, APDM System), tremorography, surface electromyography (EMG), and computerized dynamic posturography and UPDRS III. The subject will perform these assessments in the on clinical stimulation state and will repeat all or a subset of these tests in the off stimulation state. Subjects may continue these motor tests after the 12 month visit during their regularly scheduled clinic visits. Most often, this is every 3 months, however, patients may come in more or less often, depending on their clinical schedules.

For subjects already enrolled in eprotocol 25916:

Subjects who have been implanted with the Activa PC+S Neurostimulator system and who are enrolled or who have completed the Brain Radio initial study may be asked to consent to Nexus study. They will be asked to come in for additional visits (may be at follow-up if still enrolled or an additional study session.) These participants may complete the specific aims 1,2,3 listed in above protocol in addition to collecting data recordings with Nexus-D and Nexus-E systems.

These patients previously had a 'Nexus D' system, however, they will need a firmware update so that they are running Nexus-D in conjunction with Nexus-E. These patients will sign an updated consent before proceeding with the update. Nexus E Firmware Update: They will undergo a Nexus E Firmware update at their next study visit. The Nexus E firmware update will take approximately 30 minutes to perform. During the firmware update, the subject will not receive any therapeutic stimulation.

Battery life on the Activa PC + S (research device) and the Activa PC (non research device, used in standard DBS surgeries) is estimated to last for about 2-4 years. When the battery level reaches below 2.75, recording on the device is disabled in the Activa PC + S. Soon after this, the battery life will slow and the patient will need a replacement device. This is the same procedure as the standard DBS surgeries. If the patient chooses and is invited to continue in the study, they can choose to get the Activa PC + S as their replacement device, instead of a non research Activa PC device. This would allow the patient to continue in the research study with their new device.

b. Procedure Risks

The tools used for kinematic analysis are non-invasive and involve minimal risk. Physical sensors are applied to the surface of the participants body. The tests are not physically painful (other than in the removal of adhesive tape holding the sensors on the skin).

c. Use of Deception in the Study

Deception will not be used.

d. Use of Audio and Video Recordings

Audio and video recording will occur for use during data analysis, and will be copied on an encrypted hard disk locked in a cabinet in a room that is locked when unoccupied. The video recording from the video camera will be erased.

e. Alternative Procedures or Courses of Treatment

The alternative is to get the standard DBS device implanted and not participate in the study.

f. Will it be possible to continue the more (most) appropriate therapy for the participant(s) after the conclusion of the study?

Yes

g. Study Endpoint(s)

NA

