The tools used for kinematic analysis are non-invasive (do not enter your body). Physical sensors are applied to the surface of your body. The tests are not physically painful (other than in the removal of adhesive tape holding the sensors on the skin).

v. Radioisotopes/radiation-producing machines

NA

vi. Physical well-being

Low

vii. Psychological well-being

Low

viii. Economic well-being

Low

ix. Social well-being

Low

x. Overall evaluation of risk

Medium

b. International Research Risk Procedures

NA

c. Procedures to Minimize Risk

The planned procedures for protecting against and minimizing all potential risks will be the same as for the standard clinical DBS treatment delivered with the marketed version of the device. Additionally patients will be monitored for suicidal ideation and/ or intent using the Colombia Suicide Severity Scale assessment(C-SSRS). This is to evaluate and monitor risk associated with any DBS therapy and is not unique to particular use of this investigational device. Patients will undergo a baseline assessment at their first appointment and will complete the Since Last Visit version of the scale at each followup study appointment.

The C-SSRS will be reviewed and scored during each visit. If the participant has suicidal ideation and/or answers yes to any question on the Colombia suicide severity scale (questions 1-5)they will be referred by a physician to a psychiatrist immediately as per standard clinical practice.

Stimulation will be maintained at clinically recommended levels and never exceed 30 microcoulombs per square centimeter per phase.

The testing done in the laboratory brings minimal additional risks. A neurologist and a specialized nurse will be available when the testing is performed. A Monitoring Entity will verify that the investigators have adequate qualifications and resources and remain adequate throughout the trial period, that facilities, including laboratories, equipment, and staff, are adequate to safely and properly conduct the trial and remain adequate throughout the trial period.

All PHI will be stored on encrypted and password protected computers kept in locked rooms.

d. Study Conclusion

The study will terminate when 30 patients have been enrolled and tested. Participants will no longer undergo testing when their device battery runs out, if they are not reimplanted with a new Activa PC + S.

e. Data Safety Monitoring Plan (DSMC)

i. Data and/or events subject to review

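### No masking of rater or patient, and no order of runs, is specified for the adaptive versus continuous DBS comparison on the rater-judged UPDRS III

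*Protocol*

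**What the plan says.** The Brief Summary and Objective 1 (protocol section 1) both name UPDRS III first among the measures on which aDBS is compared with continuous DBS (cDBS). The summary asks whether the adaptive system "is more effective than continuous DBS on the motor Unified Parkinson's Disease Rating Scale (UPDRS III" score, alongside phenotype-specific measures. Objective 1 adds kinematic metrics.

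Item 5 of section 2.a covers the scoring in one sentence: "The clinical motor assessment of the subject will be performed using the UPDRS III scale". It names no rater.

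For Specific Aims 1b and 2b the timing is: "Outcomes will be measured after 30 minutes of aDBS or cDBS". The runs are repeated at six months in the on-medication state. No order of runs is given. For bradykinesia aDBS alone, the stimulator is updated from "10 second epochs of WFE that the PD subject will perform every 2 minutes during the 30 minute trial" (WFE is wrist flexion-extension).

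At follow-up visits patients are assessed on clinical stimulation and "will repeat all or a subset of these tests in the off stimulation state", also without mention of masking.

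Two further statements bear on feasibility. Section 9.c says "A neurologist and a specialized nurse will be available when the testing is performed". Section 2.d says "Audio and video recording will occur for use during data analysis". Neither is linked to masked rating.

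In the SAP, the primary outcome is treatment-related adverse events by stimulation condition. Its only UPDRS analysis compares Freezers with Non-Freezers on pre- and post-operative scores.

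**The concern.** UPDRS III depends on an examiner's judgement and on the patient's effort. If either knows which condition is running, expectation can move the score. The within-patient comparison removes differences between patients, but not a shift that depends on the condition. Enrolling more patients does not help either: it narrows the interval around a biased difference.

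The missing run order adds to the problem. If the order is fixed, anyone who knows it knows the condition, whatever label is used. Fatigue, practice or carry-over from the preceding run would also be mixed with the treatment contrast.

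At stake is the interpretation of the efficacy comparison that the protocol names first. A UPDRS III difference in favour of aDBS could not be separated from expectation.

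**Working it through.** **1. What the documents provide.**

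- Purpose: aDBS against cDBS on UPDRS III (protocol section 1).
- Scoring: one sentence, no rater, no masking (section 2.a, item 5).
- Timing: after 30 minutes in each condition, no order stated (section 2.a, Specific Aims 1b and 2b).
- Who controls the condition: the investigator team writes the control policies, and a PC commands stimulation on or off at a preset setting (section 1.c). No separate assessor is described.
- SAP: no masking, no run order, and no aDBS versus cDBS test on UPDRS III.

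Together these leave the state of knowledge of rater and patient undefined.

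**2. The plan's own sample size.** The SAP's only calculation concerns freezing episodes during stepping in place. The difference is 0.65 × 4.9 = 3.185. Taking 2.47 as the SD of the paired difference, the standardised effect is 3.185 / 2.47 = 1.289. A two-sided 5% paired t-test with 80% power needs n = 6.88, so 7. Allowing for 87% who freeze, 7 / 0.87 = 8.05, so 9. The stated 9 reproduces. It is not a sample size for UPDRS III, so it is not used below.

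**3. Illustration of the size.** The documents give neither a bias nor an SD for UPDRS III, so the shift is an assumption. Let b be the shift that unmasked rating adds to the mean paired difference, in units of the SD of that difference, with no true effect. The paired t statistic then follows a noncentral t distribution with n − 1 degrees of freedom and noncentrality b√n. The rejection probability is P(|T| > t(0.975, n − 1)).

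The sample sizes are 30 (where section 9.d ends the study) and 34 (the enrolment ceiling in section 8.a). For b = 0.2 and n = 30, the noncentrality is 0.2 × √30 = 1.095; for b = 0.3 it is 1.643.

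| Assumed shift b | n = 30 | n = 34 |
|---|---|---|
| 0 | 5.0% | 5.0% |
| 0.1 | 8.3% | 8.7% |
| 0.2 | 18.5% | 20.5% |
| 0.3 | 35.5% | 39.7% |
| 0.5 | 75.4% | 80.8% |

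Nearly all rejections lie in the direction of the shift: at b = 0.2 and n = 30, 18.4 of the 18.5 percentage points. The rates are higher at 34 than at 30, so a larger sample makes this worse.

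**4. What could reveal the condition.** The WFE epochs are described for bradykinesia aDBS only. Over 30 minutes that is 30 / 2 = 15 epochs of 10 seconds, or 150 seconds of movement. Unless the comparison run includes them, the task itself identifies the condition to patient and staff.

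**The case against.** The strongest reply is that silence is not open rating. A reader might infer that the team which builds and runs the algorithm scores UPDRS III knowing the condition. The documents do not say so: they name no rater and do not say what the rater knows. A design label on the title pages, which were not available here, cannot be excluded. This stands, and the point is therefore limited to what is left unspecified.

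A reader might also infer that the staff and video already in the plan make masking straightforward. That goes too far. The neurologist and nurse appear under procedures to minimise risk, as cover during testing. They are not described as raters, nor as people who can be kept unaware of stimulation. No separate computer operator is described, and filming of the UPDRS III examination is not stated.

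A third inference would be that a planned analysis is inflated. The SAP contains no UPDRS III test of aDBS against cDBS, so the rates above describe a natural analysis of the protocol's objective and not a specified one. That the bias must favour aDBS is likewise plausible but not shown.

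Finally, Objective 1 pairs UPDRS III with sensor, keyboard and force-plate measures, which largely avoid rater judgement. This is a real partial safeguard, although patient effort can still respond to knowledge of the condition. It does not protect UPDRS III itself.

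The statement in section 2.c that no deception is used is no obstacle to masking that the consent discloses.

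**Conclusion.** The concern holds in limited form. The protocol aims to compare aDBS with cDBS on a rater-judged scale, and neither document specifies masking of rater or patient or an order of runs. As written, nothing prevents scoring by someone who knows the condition.

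The consequence falls on the protocol's efficacy objective. The SAP primary outcome is not affected through UPDRS III scoring, and the SAP's Freezer versus Non-Freezer comparison is a different question.

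The size is hypothetical. With an assumed shift of 0.2 to 0.3 SD of the paired difference and no true effect, false rejection would be about 19 to 36% at n = 30 and 21 to 40% at n = 34, against a nominal 5%. The figures assume a paired t-test and complete UPDRS III pairs for all patients. This is a change worth making because it is cheap, not evidence that the results are biased.

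**What to change.** Add to protocol section 2.a, for the aDBS and cDBS runs, including the six-month repeat:

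- Runs are given in random or counterbalanced order, under coded labels known only to the person operating the PC link.
- The team member who already scores UPDRS III does not operate the link, is not told the condition and is not shown the run.
- Patients are not told the condition, and the consent discloses this.
- The 10-second WFE epochs every 2 minutes are performed in every run compared with bradykinesia aDBS.
- UPDRS III is entered before the code is opened, and the rater's and the patient's guesses are recorded and reported.

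If the UPDRS III examination is filmed, re-scoring of the items visible on video can be an optional sensitivity analysis.

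The cost is protocol and consent wording and a coded run list, with no additional assessor. One team member must be kept away from the run. The WFE epochs add about 150 seconds of movement to each affected comparison run. Masking may be imperfect, above all for the patient, who may feel stimulation change; the recorded guesses show how far it succeeded. Stimulation limits and safety cover are not affected.

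### Timed wrist-movement epochs are required only in the bradykinesia aDBS run and are not matched in its cDBS and neural aDBS comparators, so repetition is confounded with stimulation on any wrist-movement outcome

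*Protocol*

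**What the plan says.** Protocol section 1.b, Objective 2, asks whether aDBS driven by a phenotype-specific kinematic classifier does better than aDBS driven by the "resting state neural classifier and/or cDBS". Objective 1 names UPDRS III and kinematic metrics, including bradykinesia, as the measures of effect.

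Section 2.a (Specific Aim 1b and 2b) sets the common timing: "Outcomes will be measured after 30 minutes of aDBS or cDBS". It then separates the runs by how the controller is fed. "For neural and tremor aDBS, the Activa® PC+S will be updated in real time", whereas bradykinesia aDBS uses angular velocity (Vrms) from "10 second epochs of WFE that the PD subject will perform every 2 minutes during the 30 minute trial". For cDBS the section gives a duration and no task schedule.

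Three other statements in section 2.a bear on the point:

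- Item 1, on repetitive wrist flexion-extension, says "This test will assess the subject's bradykinesia state".
- The general description of the session has patients seated at rest or doing "self-paced repetitive wrist flexion-extension (WFE) for periods of 10 seconds", and allows other tasks during closed-loop stimulation.
- All subjects get practice trials in the quantitative tasks, so that they understand the goal and instructions.

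**The concern.** The movement that feeds the bradykinesia controller is also the protocol's own test of bradykinesia. Followed as written, a patient repeats that movement throughout the bradykinesia aDBS run and need not do so at all in the cDBS or neural aDBS run. If WFE is then measured, the runs differ in two respects: the stimulation strategy and the amount of recent practice or effort on the measured task. Warm-up would favour bradykinesia aDBS and fatigue would count against it.

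The difference belongs to the condition itself. Randomising or counterbalancing run order would not remove it. Nor could an analysis adjust for it afterwards, because repetition and condition coincide completely. What is at stake is whether the Objective 2 comparison in bradykinetic patients can be attributed to the classifier.

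**Working it through.** **Required exposure, from section 2.a.**

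- Epochs: 30 min ÷ 2 min = 15 (16 if one falls at both minute 0 and minute 30).
- Movement time: 15 × 10 s = 150 s (16 × 10 s = 160 s).
- Share of the run: 150 ÷ 1,800 = 8.3% (160 ÷ 1,800 = 8.9%).

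| Run | How stimulation is set | WFE epochs required |
|---|---|---|
| Bradykinesia aDBS | Vrms from timed epochs | 15 (150 s) |
| Neural aDBS | real time | none stated |
| cDBS | continuous | none stated |

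**Does other text close the gap?** The general session description offers rest or 10-second WFE as alternatives, names no run and sets no interval. The sentence on other tasks is permissive and refers to closed-loop stimulation, so it does not reach cDBS. The practice trials reduce first-exposure learning but do not equalise repetition or fatigue within a 30-minute run.

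**Possible size.** The plan has no figure to reproduce here, and the documents give no practice or fatigue effect. The following is an assumption shown over a range. Let the true stimulation effect be zero and let repetition shift the mean paired difference by δ, in units of the SD of that difference. With n patients, the paired t statistic is noncentral t with n − 1 degrees of freedom and noncentrality δ√n. The false-positive rate of a two-sided 5% test is

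P(T > t₀.₉₇₅) + P(T < −t₀.₉₇₅).

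For example, with n = 30 and δ = 0.3 the noncentrality is 0.3 × √30 = 1.643 and the critical value is 2.045, which gives 35.5%.

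| δ (assumed) | n = 10 | n = 15 | n = 30 |
|---|---|---|---|
| 0.05 | 5.2% | 5.4% | 5.8% |
| 0.1 | 5.9% | 6.5% | 8.3% |
| 0.2 | 8.8% | 11.2% | 18.5% |
| 0.3 | 13.6% | 19.1% | 35.5% |

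Thirty is the number at which section 9.d ends the study. Only patients whose kinematic classifier is the bradykinesia one are affected, and the protocol does not say how many that will be. The columns for 10 and 15 illustrate a phenotype subset.

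**Shift in the other direction.** The loss depends on the true effect. For example, with n = 30, a true effect of 0.3 SD reduced by 0.2 to 0.1 SD lowers power from 35.5% to 8.3%.

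**The case against.** **The runs may in practice be matched.** WFE is not confined to bradykinesia aDBS, and the general session text could cover every run. This stands in part. A reader might infer that patients do no WFE in the comparator runs, and the documents do not say that. They support only that matching is not required.

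**WFE as the outcome is an inference.** Section 2.a refers only to outcomes, section 2.g gives the endpoints as NA, and finger tapping is another bradykinesia measure. The SAP analyses adverse events, gait and neural measures and does not test WFE Vrms. This also stands, and it limits the point to the Aim 2 comparison when WFE is what is measured. A reader might infer that a planned SAP analysis is biased. None is.

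**The epochs are how this controller gets its signal, so they are part of the strategy.** That explains why they occur in that run. It does not prevent the same movement being made in the others without being used for control, and Objective 2 asks about the classifier.

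**Imposed movement could alter the neural run.** Its controller follows resting-state beta power, and movement-related beta change could switch stimulation. This is a real cost, though a limited one, since tasks during closed-loop stimulation are already allowed.

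**A shift of 0.2–0.3 SD in all 30 patients is not established.** Agreed. A reader who took 19–36% as the error rate would go beyond the documents, which support neither that shift nor 30 patients in this comparison.

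**Conclusion.** The concern holds in limited form. The plan requires about 150 s of WFE in the bradykinesia aDBS run and does not require it in the cDBS or neural aDBS run. A comparison on WFE therefore cannot distinguish repetition from stimulation if the protocol is followed as written.

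The imbalance in required exposure rests on the text alone. Its consequence rests on two assumptions: that WFE is measured after the run, and that repetition shifts it. Under assumed shifts of 0.05 to 0.3 SD, the false-positive rate is about 5–14% with 10 patients, 5–19% with 15 and 6–36% with 30. The lower ends are close to the nominal 5%, so the effect could be negligible, and its direction is unknown. The matter is worth correcting because the correction is cheap and the confounding cannot be undone in the analysis.

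**What to change.** Add to section 2.a that, in patients tested with bradykinesia aDBS, the same 10-second WFE epochs every 2 minutes are performed in the cDBS and neural aDBS runs. They should be logged but not used as the kinematic control signal, and outcome testing should start at the same interval after the last epoch in every run. If this is already the practice, the change is only to write it down.

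The cost is 150 s of movement in each comparator run. In cDBS this does not change the stimulation delivered. In neural aDBS, movement-related beta change may switch stimulation during the epochs, so stimulation state should be logged there and reported.

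If the sponsor prefers to keep the neural run at rest, the alternative is to match the epochs in a cDBS run used for the bradykinesia aDBS comparison, and to state that the comparison with neural aDBS on WFE is unmatched.
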